2.7.2 Deaths

Deaths will be listed by actual treatment arm including the start date of the study treatment, the last date on study treatment, the death date, and the primary cause (and contributing cause if any) for death.

2.7.3 Laboratory data

Summary statistics will be presented for absolute as well as change from baseline of laboratory hematology, blood chemistry results by visit, treatment, and laboratory test category for DB period only.

For both DB period [REDACTED] period, following analyses will be provided by treatment arm:

- the subject incidence of liver enzyme abnormalities (including AST, ALT, Total Bilirubin (TBL) and Alkaline Phosphatase (ALP))
- shift from baseline for some liver enzyme level categories (specified in the TFL shells; for e.g. $ALP \leq 1 \times ULN$)
- clinically notable laboratory values will be flagged and listed.

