### **Laboratory data**

The mean and change from baseline values of laboratory data will be summarized over time. Shift tables of the most extreme post-baseline value from baseline will be tabulated.

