Unless otherwise stated, summary tables/listings/figures will be presented for each treatment arm in the respective analysis set. In general data of interest will be listed by treatment arm and by country name/center number/subject id (/visit wherever applicable). For OLE period, data will be displayed by the treatment arm as in DB period as well as overall.

Categorical data will be presented as frequencies and percentages. For continuous data, the number of non-missing observations, mean, standard deviation (SD), median, minimum and maximum will be presented. Summary tables will also be presented by visit wherever applicable.

For efficacy endpoints, graphs will display results where it is appropriate.

General information on treatment arm handling, decimal places and other output-related information will be specified in tables, figures and listing (TFLs) shells accompanying this analysis plan.

Randomization will be stratified by prior prophylactic migraine medication treatment failure (yes vs. no) and medication overuse (yes vs. no). Stratification factors used as covariates in the analysis will use the values used for randomization unless otherwise noted.

Statistical analysis of all data will be performed using SAS® statistical software (SAS Institute, Cary, NC, USA.) version 9.4 or higher.

The full scope of analysis described below will be performed by Novartis. The unblinded IA read-out will be performed by the independent statistical analysis team outside Novartis, for the requirement of Data Monitoring Committee (DMC) meeting. The process in details are defined in DMC Charter.

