2.1.3 Visit and analysis windows

Visit window for DB period

Since the actual visit for a subject may not exactly coincide with their targeted visit date, the actual visit date is mapped to a study visit.

The next study day window will be utilized to define study visit for data captured in DB period - lab, vital signs, ECG, C-SSRS and some PROs collected during office visits ([REDACTED] BDI-II, mMIDAS) before dose is administered.

Table 2-2 Study Visit Windows

Study visit	Target Day	Study Day
Baseline	See baseline assessment of the Study (Section 2.1.1.2 , baseline definition)	
Week 4	28	16 - 43
Week 8	56	44 - 71
Week 12	84	72 - 99
Safety follow-up (for safety endpoints)	Safety follow-up should be excluded from the analysis visit windows described above and summarized under 'safety follow-up visit' for safety analyses only. Target day: last IP dose date + 12 weeks	

For safety endpoints (like lab, vital signs) except ECG, when assessment value for scheduled visit and unscheduled visit are both present within the same analysis window, scheduled visit value should be used. Unscheduled visit will only be used when there is no measurement from the scheduled visit in the defined window. In case of multiple assessment values among the same type of visit (ie, scheduled vs. unscheduled) within the same analysis window, the closest to the scheduled visit day will be used. In case of equal distances (e.g same day), the latest assessment value will be used. The exception is an assessment at early study withdrawal visits along with another assessment within a window. In such cases, the early-withdrawal assessment will be used. For ECG, the same strategy will be applied except that no prioritization of scheduled vs unscheduled visit will be made.

In case of multiple assessments on the same day for PROs (including C-SSRS), the first assessment will be used. For C-SSRS, the first complete assessment performed with the electronic version ("Since last visit" recall period) or supplemental data collected on the CRF page will be used. In case of multiple days with assessments within an analysis window (for post-baseline visit) for PROs and C-SSRS, the day the closest to the scheduled visit day will be used.

Monthly Interval for Efficacy Endpoints (from eDiary)

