 - Change from baseline in migraine-related disability and productivity as measured by modified MIDAS during the last 4 weeks of the 12-week treatment period (as defined in [Section 2.6](#))
 - Adverse events (as defined in [Section 2.7.1](#))

3 Sample size calculation

The planned total sample size in this proposed China-centric phase 3 study is 550 subjects. The key assumptions in calculating the sample size are based on prior results from erenumab global pivotal study. A treatment difference in terms of change from baseline on MMDs during Week 9-12 (primary endpoint) for erenumab 70 mg vs. placebo is assumed at -2.0 days. The common standard deviation of the primary variable is assumed at 6.8. Given a 1:1 randomization ratio among erenumab 70 mg and placebo, it requires a total of 550 subjects (including 10% drop out rate) to achieve approximate 90% power to demonstrate the treatment difference of erenumab 70 mg compared with placebo under two-sided 0.05 alpha level. The impact of spending alpha at unblinded interim analysis on sample size and power is relatively negligible. Having this interim analysis with alpha spending at 0.014 two-sided, at final analysis an observed p-value ≤ 0.046 two-sided would be required (given that the interim analysis was performed when 70% subject finished treatment or early withdraw). With that said, the overall power will be maintained at approximately 88% with planned sample size.

The sample size for Chinese sub-population will make sure the consistency of treatment effect between Chinese and total population. The methods for consistency assessment are proposed as,

$\Pr(D_{\text{China}} / D_{\text{overall}} > 0.5) > 95\%$,

which means that this China study should have high probability ($>95\%$) to demonstrate consistency where the treatment effect (treatment difference of erenumab compared with placebo) observed in the Chinese population should be as high as at least 50% of the treatment effect observed in the overall study population in the prospective trial, assuming there is no difference between the Chinese population assessed in the trial and the overall population.

To meet the above criteria, approximately 350 (out of 550 for the overall study) Chinese subjects will be recruited.

At the interim analysis, as long as China population takes the majority of the overall population, there should have high likelihood to demonstrate the consistency as well.

4 Change to protocol specified analyses

Not applicable.

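### SAP 2.7.3 plans no shift or abnormality-incidence table for 40 of the 44 protocol laboratory tests, contrary to protocol 12.5.2, and SAP Section 4 does not declare the change

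*SAP*

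**What the plan says.** The protocol, section 12.5.2 under Laboratory data, asks for means and changes over time and then states: "Shift tables of the most extreme post-baseline value from baseline will be tabulated". No test or group of tests is singled out.

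SAP 2.7.3 plans four things:

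- Descriptive tables for haematology and chemistry, double-blind period only: "Summary statistics will be presented for absolute as well as change from baseline of laboratory hematology, blood chemistry results by visit, treatment". SAP 2.1 gives their content for continuous data: "the number of non-missing observations, mean, standard deviation (SD), median, minimum and maximum will be presented".
- An incidence table: "the subject incidence of liver enzyme abnormalities (including AST, ALT, Total Bilirubin (TBL) and Alkaline Phosphatase (ALP").
- Shift tables: "shift from baseline for some liver enzyme level categories (specified in the TFL shells").
- Individual flags: "clinically notable laboratory values will be flagged and listed". The criteria, in SAP Table 5-4, cover AST, ALT, total bilirubin, alkaline phosphatase and neutrophils.

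Nothing in SAP 2.7.3 says that a shift runs to the worst post-baseline value. SAP Section 4, headed "Change to protocol specified analyses", contains only the entry that it does not apply.

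SAP 2.1.3 sets a one-value-per-window rule for safety data. For laboratory results, "Unscheduled visit will only be used when there is no measurement from the scheduled visit in the defined window".

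**The concern.** Clinical laboratory values are part of a stated secondary objective (protocol Table 2-1, SAP Table 1-1). A shift table answers a question that by-visit descriptive statistics do not: how many patients in each arm started within range and ended outside it. The SAP keeps that answer for a few liver tests and drops it for the rest, including haemoglobin, platelets, neutrophils, potassium, glucose, CPK and eGFR. A reader of Section 4 would believe that the protocol's laboratory analysis is intact.

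The unblinded interim read-out in SAP 2.12.2 takes its laboratory analyses from 2.7.3, so the same gap carries into that package.

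Vital signs were treated differently. Protocol 12.5.2 plans a count of patients with notable values, and SAP 2.7.4.2 keeps a count of patients abnormal at any post-baseline visit. Only the laboratory section lost its patient-level count for most parameters.

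**Working it through.** The documents give no figure on this point, so there is none to reproduce. The check is a count from protocol Table 8-3 set against SAP 2.7.3.

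**Tests collected**

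- Haematology, main panel: RBC, nucleated RBC, haemoglobin, haematocrit, MCV, MCH, MCHC, RDW, reticulocytes, platelets, WBC = 11.
- Haematology, differential: bands, neutrophils, eosinophils, basophils, lymphocytes, monocytes, myeloblasts, promyelocytes, myelocytes, metamyelocytes, atypical lymphocytes = 11.
- Chemistry: 14 from sodium to alkaline phosphatase, with direct and total bilirubin counted separately, plus 8 from ALT to eGFR = 22.
- Total: 11 + 11 + 22 = 44.

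**Tests with a shift or incidence table in SAP 2.7.3**

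- Named: AST, ALT, total bilirubin, alkaline phosphatase = 4. The shift tables cover only some liver categories, so 4 is an upper limit for shifts among the named tests.
- Without either table: 44 − 4 = 40, made up of 22 haematology and 22 − 4 = 18 chemistry tests.
- Bilirubin counted once: 43 − 4 = 39 of 43.
- The incidence item introduces its tests with the word including. If direct bilirubin were also meant, the figure would be 44 − 5 = 39 of 44.

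**Tests with no notable-value criterion either**

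- Table 5-4 adds neutrophils to the four liver tests, so 44 − 5 = 39. Notable neutrophil values are listed by patient but not counted in a table.

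**What the remaining tables can show.** Suppose, purely as an illustration, that three patients in one arm each lost 200 × 10⁹/L of platelets by the same visit. The minimum change for that arm would be −200 or lower, so the fall would be visible. The table would not say whether one patient or three had it, or whether they started within range.

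**Window rule.** Protocol Table 16-3 requires some liver repeats within 48 hours or within the next week. A repeat up to 7 days after a Day 84 sample falls by Day 84 + 7 = 91, inside the Week 12 window of Days 72 to 99 (SAP Table 2-2). Under SAP 2.1.3 the scheduled value would be the one analysed even if the repeat were worse. Whether this reaches the liver incidence and shift tables depends on whether 2.1.3 governs them, and the SAP does not say.

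**The case against.** The strongest reply is that much of the information survives. All 44 tests receive by-arm, by-visit summaries with minimum and maximum. Under protocol 10.1.1, an abnormal result that causes symptoms, needs therapy or is judged clinically significant is an adverse event. SAP 2.7.1 tabulates adverse events by arm, and treatment-emergent events also by maximum CTCAE grade. A reader might infer that individual laboratory toxicity in the 40 tests never reaches a by-arm table. The documents do not support that, and this part of the reply stands. It does not close the gap: a minimum or maximum neither counts patients nor ties them to baseline, and the adverse event route depends on symptoms, treatment or the investigator's judgement.

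Sampling is also sparse. As far as the extracted layout of protocol Table 8-1 can be read, chemistry and haematology are drawn at screening, Day 1, end of treatment and safety follow-up, and not at Weeks 4 or 8. By-visit extremes are therefore close to the worst scheduled values. That is fair, but it limits only the worst-value part of the loss. The patient count is still missing.

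Both documents say that the liver tests and neutrophils were chosen as potentially sensitive to the drug. This could justify a reduced set, but the SAP does not offer it as a reason for departing from the protocol. The 44-test denominator also gives minor indices the same weight as clinically important tests, so the fraction describes coverage and not clinical importance.

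A reader might also infer that 2.1.3 hides worse repeat results. That is only a conditional risk. Where a window holds no scheduled sample, the unscheduled value is used. If a repeat follows an abnormal scheduled value, the patient already counts as abnormal and only the severity category could change.

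Finally, the table shells and the DMC charter are not available here. The shells might contain more tables, although 2.7.3 cites them only for the liver categories. What the DMC receives in its regular safety reviews cannot be judged from 2.7.3 alone.

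**Conclusion.** The concern holds as a protocol-to-SAP discrepancy. A planned safety analysis has been cut from all laboratory tests to at most four named liver tests, its worst-value rule has been lost, and Section 4 does not say so. The size is 40 of 44 tests, or 39 of 43 with bilirubin counted once. The consequence is a missing count by arm of patients whose measured values shift from baseline. Laboratory extremes are not invisible.

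This rests on the SAP text as the full statement of planned laboratory outputs, and on reading the unrestricted protocol sentence as covering every haematology and chemistry test. The 2.1.3 point is an ambiguity to settle, not a demonstrated loss. Neither the primary nor any secondary efficacy result is touched, but a stated safety endpoint is reported less fully than the protocol promised, and correcting this is cheap.

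**What to change.** In SAP 2.7.3, add by-arm shift tables from baseline to the worst post-baseline value for every haematology and chemistry test, for example low/normal/high against the laboratory's reference range. State that these tables and the liver abnormality incidence draw on all post-baseline results, including unscheduled and repeat tests, and confine the 2.1.3 window rule to by-visit summaries. The low/normal/high scheme and the explicit rule on unscheduled results are sensible additions; the protocol does not spell them out.

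If the sponsor keeps the reduced set, Section 4 should name the departure from protocol 12.5.2 and give the reason.

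Cost: a few lines of SAP text and one standard table family. No new data are needed.

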2.7.4 Other safety data

2.7.4.1 ECG and cardiac imaging data

The ECG measurements from this clinical study will be performed as per standard of care for routine safety monitoring, rather than for purposes of assessment of potential QTc effect.

Subject incidence of abnormal ECG diagnosis (see [Table 5-5](#)) will be summarized by treatment group and by visit.

However, since these evaluations may not necessarily be performed under the rigorous conditions expected to lead to meaningful evaluation of QTc data, these data are not expected to be useful for meta-analysis with data from other trials.

2.7.4.2 Vital signs and weight

The analyses of vital signs (systolic/diastolic blood pressure, pulse rate) and weight will include summary statistics of change from baseline by treatment group and by visit for DB period.

The number and percentage of subjects with clinically relevant abnormality (see [Table 5-3](#)) at any post-baseline visit will be presented for both DB period [REDACTED].

The number and percentage of subjects with hypertension/worsening hypertension or elevated blood pressure at post-baseline will be provided by as change from baseline in category of with/without hypertension or elevated blood pressure at baseline.

- Hypertension at baseline will be identified from medical history based on SMQ narrow list
- Elevated blood pressure at baseline is defined as Systolic Blood Pressure (SBP) ≥ 140 mmHg or Diastolic Blood Pressure (DBP) ≥ 90 mmHg

- Hypertension/worsening hypertension at post-baseline will be identified from AE based on SMQ narrow list
- Elevated blood pressure at post-Baseline is defined as two consecutive visits meeting increase of ≥ 20 mm Hg in SBP or increase of ≥ 15 mm Hg in DBP

2.7.4.3 Columbia-Suicide Severity Rating Scale (C-SSRS)

C-SSRS will be collected during DB period and safety follow-up period.

The number and percentage of subjects reporting any suicidal ideation or any suicidal behavior will be summarized descriptively by treatment group and by visit.

Shift table of C-SSRS maximum severity of suicidal ideation/behavior compared to baseline will be provided by treatment group by visit.

No statistical testing will be performed on C-SSRS.

2.7.4.4 Anti – AMG 334 Antibody Formation - Immunogenicity (IG) analysis set

The number and percentage of subjects who are positive for anti-AMG 334 antibodies at baseline (Day 1, pre-dose) and who develop anti-AMG 334 antibodies (binding and, if positive, neutralizing) at any time during the DB period (after signing informed consent and up to the end of DB period or safety follow-up) will be tabulated by treatment group.

In addition, the number and percentage of subjects who develop anti-AMG 334 antibodies at any time post-dose will be tabulated by treatment group.

The list of subjects with positive at any time will be provided.

The Immunogenicity prevalence set includes all subjects in the Full analysis set with a determinant baseline IG sample **or** at least one determinant post-baseline IG sample.

The Immunogenicity incidence set includes all subjects in the Immunogenicity prevalence set with a determinant baseline IG sample **and** at least one determinant post-baseline IG sample.

2.7.4.4.1 Sample anti-drug antibody (ADA) status

Each ADA sample is assessed in a two tiered ADA testing approach. All ADA samples are analyzed in the initial screening assay (first tier). Samples testing positive in the screening assay are then subjected to a confirmatory assay to demonstrate that ADA are specific for AMG334 (second tier). Samples identified as positive in the confirmatory assay are considered ADA positive and are further characterized in the neutralization assay to indicate the presence of neutralizing antibodies (NAb).

The following properties of each sample will be provided in the source data:

- Positivity in confirmatory assay according to pre-specified confirmatory cut point: ADA positive (yes) or ADA negative (no)
- Presence of NAb: yes or no

Sample ADA status will only be listed. It is determined based on the following definitions:

- ADA-negative sample: Determinant sample where ADA screening or confirmatory assay is negative.
- ADA-positive sample: Determinant sample where ADA confirmatory assay is positive.
- ADA-positive NAb sample: Determinant sample where NAb ADA assay is positive.

The following definitions apply only to post-baseline ADA-positive samples with a corresponding determinant baseline sample:

- Treatment-induced ADA-positive sample: ADA-positive sample post-baseline with ADA-negative sample at baseline.
- Treatment-boosted ADA-positive sample: ADA-positive sample post-baseline with signal greater than the ADA-positive baseline signal.

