### **8.5.5 AMG 334 Antibody testing**

Blood samples for antibody testing are to be collected for the measurement of anti-AMG 334 binding antibodies. Samples will be collected at the timepoints defined in [Table 8-1](#), prior to study drug administration. Samples testing positive for binding antibodies will also be tested for neutralizing antibodies and may be further characterized for quantity/titer, isotype, affinity, and presence of immune complexes. Additional blood samples may be obtained for further evaluation of anti-AMG 334 antibodies during the study.

Sites will not be notified of positive neutralizing antibody results to the investigational product for a subject prior to that subject's final scheduled study visit and the subjects with a positive neutralizing antibody response will continue to be dosed during the course of study.

During the **COVID-19 pandemic** that limits or prevents on-site study visits, or if visits by site staff to a subject's home are not feasible, the collection of samples may be modified by Novartis and will be communicated to the investigator.

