2.7.4.4.2 Subject ADA status

The following overall summaries will be provided using the Immunogenicity incidence set:

- Treatment-boosted ADA-positive: number and percent of subjects with at least one treatment-boosted ADA-positive sample. The denominator is the number of subjects with an ADA-positive sample at baseline.
- Treatment-induced ADA-positive: number and percent of subjects with at least one treatment-induced ADA-positive sample. The denominator is the number of subjects with an ADA-negative sample at baseline.
- ADA-negative: number and percent of subjects with no treatment-induced or treatment-boosted ADA-positive sample.
- ADA incidence (i.e. % ADA-positive): number and percent of subjects with at least one treatment-induced or treatment-boosted ADA-positive sample.

The following summaries, both overall and by time point (including baseline), will be provided using the Immunogenicity prevalence set. For summaries by time point, the denominator is the number of subjects at that time point with determinant samples:

- ADA prevalence: number and percent of subjects with at least one ADA-positive sample.
- NAb ADA prevalence: number and percent of subjects with at least one ADA-positive NAb sample.

A listing will be provided by subject with supporting information (i.e. ADA sample status at each time point (including positive samples) and subject ADA status

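### The rule for a treatment-boosted antibody sample has no margin for assay variability, and the source data listed beside it do not include the signal it compares

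*SAP*

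**What the plan says.** SAP 2.7.4.4.1 describes tiered testing (screening, confirmation, then neutralization for confirmed positives) and introduces the data to be received with "The following properties of each sample will be provided in the source data". Two items follow. One is the confirmatory result as positive or negative; the other is "Presence of NAb: yes or no". No signal, titre or other quantity is listed.

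The section then defines two kinds of post-baseline positive sample:

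- Induced: "Treatment-induced ADA-positive sample: ADA-positive sample post-baseline with ADA-negative sample at baseline". This needs only the yes/no results.
- Boosted: "ADA-positive sample post-baseline with signal greater than the ADA-positive baseline signal". This needs a quantitative result at both times. The text does not say which assay's signal is meant and sets no minimum increase.

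SAP 2.7.4.4.2 carries both into the subject-level summaries. ADA incidence is the "number and percent of subjects with at least one treatment-induced or treatment-boosted ADA-positive sample". ADA-negative is the complement: subjects with neither kind of sample. For the boosted count on its own, "The denominator is the number of subjects with an ADA-positive sample at baseline".

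Protocol 8.5.5 leaves quantification optional: samples positive for binding antibodies "may be further characterized for quantity/titer, isotype, affinity, and presence of immune complexes". Anti-AMG 334 antibodies are part of the secondary safety endpoint in Protocol Table 2-1 and SAP Table 1-1.

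**The concern.** A repeat measurement of an unchanged antibody level will fall above or below the first one through assay variation alone. A rule that accepts any increase turns that variation into a classification. For a baseline-positive subject the boosted rule is the only thing that decides the label. If the later reading is slightly higher, the subject is an incident case; if it is slightly lower, the same subject is counted as ADA-negative. Neither label describes a stable pre-existing antibody.

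There is also a gap between rule and data. Applied to the listed source properties alone, the boosted definition cannot be evaluated. Someone would have to decide later which signal to request and how to compare it, and that decision would not be pre-specified.

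At stake is a descriptive safety summary. Protocol 4.5 describes erenumab immunogenicity as low in incidence, so a few misclassified subjects could be a visible fraction of the reported rate.

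**Working it through.** The plan states no figure for ADA incidence, baseline positivity or assay precision, so there is no figure to reproduce. Two checks apply.

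**Check 1: which summaries can be derived from the listed yes/no results?**

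| Summary (SAP 2.7.4.4.2) | Needs a signal? |
|---|---|
| Treatment-induced | No |
| ADA prevalence | No |
| Neutralizing-antibody prevalence | No |
| Treatment-boosted | Yes |
| ADA incidence | Only for baseline-positive subjects |
| ADA-negative | Only for baseline-positive subjects |

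**Check 2: how often does the rule call an unchanged subject boosted?**

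Inputs:

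- Number of post-baseline samples, k. Protocol Table 8-1 schedules antibody samples on Day 1, at End of Treatment and at Safety Follow-Up. Footnote 4 requires Safety Follow-Up only of subjects who discontinue double-blind drug or do not continue into the open-label period. So k = 1 for open-label entrants and up to 2 for others.
- Assumptions: no true change, a continuous signal without ties, baseline and later readings exchangeable, and every later sample still confirmed positive.

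Under exchangeability each of the k + 1 readings is equally likely to be the largest. The subject escapes the boosted label only if the baseline reading is the largest:

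P(boosted) = 1 − 1/(k + 1) = k/(k + 1)

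- k = 1: 1/2 = 50%
- k = 2: 2/3 = 66.7%

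The result does not depend on assay precision. A simulation with lognormal error at assumed coefficients of variation (CV) of 10%, 20% and 30% gave 50% and 66.7% throughout.

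**Effect on ADA incidence.** Let p be baseline positivity and r the induced rate among baseline-negative subjects, both assumed. Chance boosting adds p × k/(k + 1). Its share of reported incidence is that amount divided by r(1 − p) + p × k/(k + 1). The figure of 275 per arm (SAP 1.1) is used only for scale, and r is set at 3%.

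| Assumed p | Baseline-positive per 275 | Added to incidence, k = 1 to k = 2 (percentage points) | Share of incidence at r = 3% |
|---|---|---|---|
| 0.5% | 1.4 | 0.25 to 0.33 | 8 to 10% |
| 1% | 2.8 | 0.50 to 0.67 | 14 to 18% |
| 2% | 5.5 | 1.0 to 1.3 | 25 to 31% |
| 5% | 13.8 | 2.5 to 3.3 | 47 to 54% |

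Worked row, p = 1%: the induced part is 0.03 × 0.99 = 2.97%. Chance boosting adds 0.01 × 0.5 = 0.50 to 0.01 × 2/3 = 0.67 points. The total is 3.47% to 3.64%, of which 14% to 18% is noise. Over r from 1% to 6% and the same range of p, the share runs from 4% to 78%.

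**If no signal is available**, incidence can still be bounded. At p = 1% and r = 3% it lies between 2.97% (none boosted) and 2.97% + 1% = 3.97% (all boosted).

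**Effect of a margin.** In the same simulation with two post-baseline samples, a 2-fold minimum cuts the false boosted rate from 66.7% to about 0%, 1.3% and 8.4% at CVs of 10%, 20% and 30%. A 4-fold minimum brings it to at most 0.1%.

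**The case against.** A reader might infer that ADA incidence as a whole is either impossible to derive or driven by assay noise. The documents do not support that. The induced component uses only yes/no results, and only baseline-positive subjects are exposed to the boosted rule. Noise would dominate incidence only if baseline positivity were high relative to the induced rate, and neither figure is given.

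Several further objections stand:

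- The SAP does not say its list of source properties is exhaustive, and the boosted definition presupposes a signal. The laboratory may well transfer one. That answers the data gap but leaves the missing margin.
- The 50% and 67% are upper values. A titre reported in dilution steps will often tie, and a tie is not an increase. A subject who later tests negative cannot be boosted. Open-label entrants have one scheduled post-baseline sample, not two.
- The low-immunogenicity statement in Protocol 4.5 concerns erenumab treatment. It says nothing about pre-existing antibodies and cannot anchor the assumed baseline rates.
- Boosted and induced subjects are reported separately with their own denominators, baseline positivity is tabulated (SAP 2.7.4.4), and a subject listing is planned. A careful reader could see how much of incidence comes from boosting.

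A reader might also infer a bias between arms. None is shown. Under no true change the rule acts equally in both arms, the number of samples follows open-label entry and not randomized treatment, and SAP 2.7 plans no between-group safety tests.

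These points limit size and reach. They do not remove the defect: the stated rule labels an unchanged antibody level as a response about as often as not.

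**Conclusion.** The concern holds for subjects who are antibody-positive at baseline. For them the boosted label, and through it the choice between ADA-incident and ADA-negative, rests on a comparison with no margin and on a quantity missing from the listed data. With a continuous signal, no true change and persistent positivity, the chance of a false boosted label is 50% with one post-baseline sample and up to 67% with two.

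The absolute effect is illustrative because the documents give no baseline positivity. At an assumed 1%, with all baseline-positive subjects staying positive, it is 0.5 to 0.67 percentage points of ADA incidence per arm, or roughly 1.4 to 1.8 subjects in 275 (2.75 × 1/2 and 2.75 × 2/3). Induced ADA, both prevalence summaries and the efficacy analyses are untouched. It should be corrected because the rule as written misclassifies and the correction is small.

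**What to change.** In SAP 2.7.4.4.1:

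1. Name the quantitative measure used for boosting: which assay's signal, or titre where available.
2. Add that measure to the listed source data for every confirmed-positive sample, including baseline.
3. Define boosted as an increase over baseline of at least a pre-specified multiple that exceeds the validated assay variability. The multiple should come from the assay validation, which the documents do not report, and be fixed before unblinding.

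If no quantitative result will be transferred, remove the boosted category, report treatment-induced ADA as the incidence measure, and list baseline-positive subjects separately. The ADA-negative definition in SAP 2.7.4.4.2 should then be reworded so that a stable baseline-positive subject is not counted as negative.

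The cost is a few lines of SAP text and one extra field in the laboratory transfer for a subset of samples. Protocol 8.5.5 already permits quantification, so titre need not be made mandatory and no protocol amendment is needed. The downside is that a small true increase below the margin will not be called boosted.
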